The study is also feasible for enrollment over 9 months, with 3 months follow-up based on volume of the clinics at UF and Nemours. Specifically, the three adult GI providers at UF Health who will be participating in this trial will enroll patients from 10 clinics/wk, which represents approximately 150 patients/wk. Of these, approximately 40% of patients are being seen for peptic acid/GERD indications which should produce 50-60 pts/week that meet inclusion criteria. Assuming only half of eligible patients consent to the study, we anticipate enrolling the 350 adults within a 12 week period. For 2014 and 2015 providers in the Division of Gastroenterology at the Nemours Children's Hospital saw 722 and 877 pediatric patients, respectively, who received a prescription for a PPI. For those years 1207 and 1525 respective prescriptions were written for a PPI. Currently the Division sees 20-30 pediatric patients/week that meet the inclusion criteria. Assuming we see 20 patients/week, we expect to enroll at least one-third to one-half of them, which would allow enrollment of 250 patients 6-9 months.

Recent data suggests that in a period of 6-9 months, approximately 60 patients will meet criteria and be enrolled in the study at Nemours Children's Hospital (NCH) alone. In a period of one month (June-July 2016), on average, 71% of PPI prescriptions were performed at GI Clinics from the Nemours Health System (i.e LKM, 1717 ORL, MELB, Lake Nona-NCH) and the remaining were prescribed in other clinics such as

LKM Otolaryngology Clinic and others. At NCH, on average, 38 % of the patients prescribed with a PPI therapy are prescribed at NCH GI Clinic alone. (**Table 4**)

Table 4. PPI prescriptions in a month at Nemours, Orlando

	Unique MRNs	PPI prescribed at GI Clinics	PPI prescribed at other clinics*	PPI prescribed at NCH GI Clinic
Week 1	33	24	9	10
Week 2	34	24	10	15
Week 3	25	16	9	10
Week 4	48	36	12	18

\*i.e. LKM Pulmonology, MLB Reumatology, NCH Nephrology, NCH Neurology, NCH orthopedics, NCH Otolaryngology, LKM Otolaryngology, NCH, Allergy/Inmunology, NCH, Plastic Surgery, 1717 ORL Genetics, NCH Nutrition, 1717 ORL Oncology, 1717 ORL Nephrology, 1717 ORL Otoralyngology, others

In order to improve enrollment efforts, Spartan RX genetic testing equipments will be required at Nemours satellite GI Clinics (i.e. LKM, MELB, 1717 ORL).

Study Design. The study is a randomized, open-label, comparative effectiveness clinical trial in 180 patients (60 children, 120 adults) with GERD or any stomach acid mediated condition that will require a PPI. Patients will volunteer to be randomized to either conventional PPI treatment or genotype-supported PPI treatment. All participants will have symptoms of GERD or related diseases who are candidates for PPI therapy or who are on PPI therapy and classified as refractory GERD. Adult patients will be enrolled at UF Health Gastroenterology Clinics and children will be enrolled at the Nemours Children's Hospital Gastroenterology Clinics. After obtaining informed consent, participants will be genotyped and randomly assigned to either conventional treatment or genotype-supported PPI therapy using a randomization table. At NCH, study participants in the control/conventional arm will be blinded on CYP2C19 metabolizer status. Study staff members will not be blinded to any study procedures or determinations as this will improve and facilitate study feasibility. At the end of study period (i.e. 8-12 weeks) study participants in the control/conventional arm will be revealed of metabolizer phenotype status. We will also collect data from the health records for up to 24 months after enrollment on upper respiratory infection (cold), sore throat, strep throat, bronchitis, pneumonia, ear infection, acute sinusitis (sinus infection), bone fractures, renal function, and gastrointestinal infections for preliminary assessment of the effects of CYP2C19-supported PPI dosing on adverse effects.

Participation stipends. Each participant will receive \$25 dollars at the end of study participation. Participants must have completed all study procedures by the end of the study period in order to receive the complete study stipend. If a study participant decides to withdraw from study before the end of study period (before 3 months), the participant will receive a pro-rated stipend. A deposit will be provided in a single CT Payer master card. Each participant will be provided a CT Payer (master card) at the moment of consent. The CT Payer card will be uploaded with the stipend at the end of study participation. Participants whom insurance coverage is limited, a separate deposit will be provided to cover study therapy expenses. We expect to incur in study drug expenses for participants with higher PPI dose prescriptions than conventional dosing (i.e. RMs and UMs).

**Dosing.** All participants will be genotyped and those randomized to the conventional arm will be dosed according to FDA product labeling. At Nemours, for those randomized to genotype-supported arm, the treating clinician will be provided dosing recommendations with the dosing recommendations based on CYP2C19 genotype-inferred metabolizer phenotype. Specifically, for participants classified as PM and IM we will recommend that their conventional (based on NM phenotype) PPI doses be reduced 50% (halved). We will recommend that conventional PPI doses be increased 50% and 100% for RMs and UMs, respectively. For participants with the \*2/\*17 diplotypes we recommend they be dosed as NMs. At UF Health, the PMP Committee will convene with the GI clinicians to evaluate and approve and or modify the recommendations for adults. Treatment will be 8-12 weeks. At NCH, clinical support in regards to PPI recommended dosing per CYP2C19 metabolizer phenotype will be provided to GI physicians in EPIC (EMR system). High PPI doses will be aligned with current clinical practices by doubling the original dose..

**Table 5.** PPI dosing guide per metabolizer phenotype

Metabolizer Phenotype	PPI recommended dosing
NM or Inconclusive (Conventional dosing)	Esomeprazole (Nexium) <10 kg: 5 mg daily; 10-20 kg: 10 mg daily; > 20 kg: 20 mg daily Lansoprazole (Prevacid) <15kg: 7.5mg daily; 15-30 kg: 15 mg daily; > 30 kg: 30 mg daily Omeprazole (Prilosec) <10 kg: 5 mg daily; 10-20 kg: 10 mg daily; > 20 kg: 20 mg daily Pantoprazole (Protonix) <10 kg: 5 mg daily; 10-20 kg: 10 mg daily; > 20 kg: 20 mg daily
PM or IM (50%↓ of Conventional dosing)	Esomeprazole (Nexium) <10 kg: 2.5 mg daily; 10-20 kg: 5 mg daily; > 20 kg: 10 mg daily Lansoprazole (Prevacid) <15kg: 3.75mg daily; 15-30 kg: 7.5mg daily; > 30 kg: 15mg daily Omeprazole (Prilosec) <10 kg: 2.5 mg daily; 10-20 kg: 5 mg daily; > 20 kg: 10 mg daily Pantoprazole (Protonix) <10 kg: 2.5 mg daily; 10-20 kg: 5 mg daily; > 20 kg: 10 mg daily
RM (50% ↑ of Conventional dosing)	Esomeprazole (Nexium) <10 kg: 7.5mg daily; 10-20 kg: 15 mg daily; > 20 kg: 30 mg daily Lansoprazole (Prevacid) <15kg: 11.25mg daily; 15-30 kg: 22.5mg daily; > 30 kg: 45mg daily Omeprazole (Prilosec) <10 kg: 7.5 mg daily; 10-20 kg: 15 mg daily; > 20 kg: 30 mg daily Pantoprazole (Protonix) <10 kg: 7.5 mg daily; 10-20 kg: 15 mg daily; > 20 kg: 30 mg daily
UM (100% ↑ from Conventional dosing)	Esomeprazole (Nexium) <10 kg: 10 mg daily; 10-20 kg: 20 mg daily; > 20 kg: 40 mg daily Lansoprazole (Prevacid)

	
<15kg: 15mg daily; 15-30 kg: 30 mg daily; > 30 kg: 60mg daily
 
Omeprazole (Prilosec)
 
<10 kg: 10 mg daily; 10-20 kg: 20 mg daily; > 20 kg: 40 mg daily
 
Pantoprazole (Protonix)
 
<10 kg: 10 mg daily; 10-20 kg: 20 mg daily; > 20 kg: 40 mg daily

--	---

**CYP2C19 genotyping.** Genotyping at UF will be done by the UF Pathology Laboratory, as has been done for over 1,600 patients in the UF Health CYP2C19-clopidogrel implementation, with laboratory results reported in the same way, and clinical decision support built into the EHR in the same manner as was done for clopidogrel, but specific to the PPIs. Nemours Children’s Hospital, will genotype using the Spartan RX system. Spartan RX is a novel genotyping platform recently approved by the FDA as an in-vitro diagnostic that will interrogate \*2, \*3 and \*17 CYP2C19 using saliva samples. Two of these rapid turnaround (approx. 1 hour) platforms reside in Nemours Children’s Hospital (NCH) in Orlando and are supervised by [name], Chair of Pathology and Director of the CLIA approved Clinical Lab.

CYP2C19 genotyping on the Spartan RX system has been validated to meet all CLIA/CAP requirements at Nemours Children’s Hospital and the platforms are currently being used in a pilot program funded by NCH to implement PGX testing at NCH with plans for dissemination to all Nemours sites in the Nemours Children’s Health System. The Implementation Program is led by the two Nemours co-PIs of this project, [name] and [name].

Additionally, CYP2C19 genotyping will also be performed at the CLIA certified laboratory in the Alfred I DuPont Hospital in Delaware under the supervision of [name], B.S.. There are two possible scenarios where study samples will be analyzed in Delaware: (1) study saliva sample has been collected at a Nemours Satellite Clinic (i.e. Melbourne, Lake Mary, 1717 Orlando) including Nemours Children’s Specialty Care Clinic at Jacksonville, FL (Downtown and South Clinics)- Oragene OGR-575 saliva collection kits from DNA Genotek. Inc, previously used in studies by [name] and [name], will be used instead of Spartan Rx equipment; and (2) extra saliva sample collected will be analyzed as a back-up system if Spartan Rx provides Inconclusive genotype results. Remaining saliva sample will continue to be stored for future research when consent has been provided. Expected turnaround time is ± 1 week from collection.

**Sample storage for future genotyping/sequencing.** We will collect an additional saliva (at NCH) or blood sample (at UF) in order to identify less frequent loss- of-function SNPs or for genotyping or sequencing for future research. At NCH, future samples will be stored at the Nemours Center for Pharmacogenomics and Translational Research in Jacksonville FL under [name] direct supervision.

Inclusion Criteria. At NCH, boys and girls 5 to 17 years old diagnosed with GERD or any other stomach acid mediated condition for which a PPI treatment is provided, will be considered for the pediatric arm. Patients are currently under a Proton Pump Inhibitor (PPI) therapy or will start a PPI therapy. Parents/legal guardians and or child must have access to internet and a valid email address in order to complete weekly required study forms. For adults, any patient over the age of 17 who presents to GI clinic with GERD symptoms and is either 1) being initiated on PPI therapy or 2) continue to have symptoms despite PPI therapy will be considered eligible for the study.

Exclusion Criteria. This study will exclude participants who have had extensive esophageal or gastric surgery; and any major chronic illness or conditions that in the opinion of the gastroenterologist that would interfere with participation in the study. At NCH, patients with a history of Phenylketonuria (PKU) and patients with a history of previous adverse effects from PPI treatment or sensitivity to aspartame (NutraSweet, Equal) will be excluded from study. In addition, parents/legal guardians who are non-adherent including inability or unwillingness to provide consent or unwillingness of the child to provide assent(when required), who are unable to take study medications, who are unable to communicate via telephone or other device, who do not have access to a computer with internet access; will be excluded from study participation. No pregnancy test will be obtained from girls in childbearing years as PPI therapy has been demonstrated to be not harmful for pregnancy.

Participant Recruitment Methods. Physicians at UF Health participating clinics will be approached by the study team for involvement in the research protocol. Physicians who agree to participate in this study will be educated on the study protocol and the interpretation of CYP2C19 genotyping. Physicians will participate in surveys that assess their opinions and behaviors as it relates to pharmacogenetics. Patients (or in the case of children, the pediatric patient and their parent/legal guardian) will be approached for participation after a clinical assessment has been performed by a GI provider during a GI clinical appointment. GI providers will notify study coordinator on patient eligibility. Study procedures will be performed after obtaining proper consent and/or child assent. .

In addition, the clinic schedule will be reviewed each week for potential participants. If possible, patients or families will be contacted ahead of time to determine their interest in the study, should they qualify for participation.

Genetic results and clinical decision support. Results will be entered in the participant's electronic health record; genotype results for participants in the control/conventional arm will not be made available to patients/families through the secure patient portal in the EMR to maintain blind status. PPI recommended dosing will be made available to GI providers in the EMR for genotype-guided dosing. PPI templates will include phenotype, genotype, dosing recommendations, and educational information. Participants in the conventional arm will be prescribed the conventional PPI dose.

To minimize risks associated with genetic studies, all results of genetic tests and patient data will be stored in a secure database which is accessible only to study investigators. Genotype and phenotype data will be stripped of all identifiers prior to submission to the NIH dbGAP repository.

Assessment of PPI adverse events and efficacy. Our primary outcome will be a directed interview and questionnaire by study personnel at baseline and every following week up to 12 weeks of participation for efficacy of PPI therapy and for adverse outcomes for the study period: upper respiratory infection (cold), sore throat, strep throat, bronchitis, pneumonia, ear infection, acute sinusitis (sinus infection), and gastroenteritis. We have experience using the questionnaire to evaluate the safety of PPI treatment in children. The prevalence of each respiratory and gastrointestinal symptom will be compared in participants receiving conventional vs. genotype-supported dosing. As secondary outcomes, the efficacy and safety (adverse event score) of PPI therapy will be determined from scores from patient and parent-proxy reported outcomes: the GASP-Q, the validated SN-5 Pediatric Sinonasal Symptom Survey and validated PedsQL™ Gastrointestinal Symptoms Module. Efficacy and adverse events questionnaires will be completed via an electronic questionnaire on a weekly basis and stored in REDCap.

At Nemours Children's Hospital continuous monitoring on study metrics will be offered by study staff. Study metrics will include Gasp-Q, PedsQL™ Gastrointestinal Symptoms Module, SN-5 Pediatric Sinonasal Symptom Survey and Safety Q.

- Gastrointestinal problems under scope includes; stomach pain and hurt; stomach upset; food and drinks limits; trouble swallowing; heartburn and reflux; gas and bloating; constipation; diarrhea; worry; medicines and communication will be measured.
- On the other hand; sinus infection; nasal obstruction; allergy symptoms; emotional distress; activity limitations and overall quality of life are some of the metrics to be evaluated for sinus and/or nasal problems.
- Each metric has its own scoring scale. Gastrointestinal problems will range from 0-100 for "Never" to "Almost always", respectively. Sinus and/or nasal problems have a 1-7 scale for "None of the time" to "All of the time", respectively.
- Safety Assessment (adverse event score) of PPI therapy will be scores from a questionnaire comprised of 7 respiratory symptoms: upper respiratory infection (cold); sore throat; strep throat; bronchitis; pneumonia; ear infection; acute sinusitis (i.e. sinus infection)

Monitoring for adverse events will be performed by the treating medical staff, the Principal Investigators, the site investigators, and the research coordinator(s). We will follow the guidance from the Office for Human Research Protections (OHRP) DHHS: Guidance on Reviewing and Reporting unanticipated Problems Involving Risks to Subjects or Others and Adverse Events <http://www.hhs.gov/ohrp/policy/AdvEvntGuid.htm>. Any event that: (1) involves harm, or an increased potential for harm, to one or more participant(s), or others, AND (2) is unexpected, AND (3) is related, or probably related, to study procedures will be reported to the Nemours and or UF IRB within 5 days of discovery, or within 24 hours if an unforeseen death. We will follow FDA guidelines for report of adverse events to the FDA within the required timeframe for the event. Additional standard institutional IRB reporting guidelines for adverse event reporting will also be followed.

There is no Data and Safety Monitoring Board (DSMB) for this project as the medications being prescribed are part of routine clinical care. Additionally, the study is a pragmatic trial design and there are no required actions by the clinicians based on the genotypes returned. All study staff will report any unanticipated problems to the principal investigators who will determine if reporting to the IRB is required. No Investigational New Drug (IND) form will be filled as there is no increased risk of adverse effects by increasing PPI dose based on genotype and our study does meet the exemption criteria for an IND submission as described below:

- (i) The investigation is not intended to be reported to FDA as a well-controlled study in support of a new indication for use nor intended to be used to support any other significant change in the labeling for the drug;
- (ii) (ii) If the drug that is undergoing investigation is lawfully marketed as a prescription drug product, the investigation is not intended to support a significant change in the advertising for the product;
- (iii) (iii) The investigation does not involve a route of administration or dosage level or use in a patient population or other factor that significantly 1 D46.0000 increases the risks (or decreases the acceptability of the risks) associated with the use of the drug product;
- (iv) (iv) The investigation is conducted in compliance with the requirements for review by an IRB (21CFR56) and the requirements for informed consent (21CFR 50); and
- (v) (v) The investigation is conducted in compliance with the requirements of 21CFR312.7 (Promotion and sale of investigational drugs).

Metrics for assessing success of pharmacogenetic testing in clinical practice. We will test a variety of variables that will provide insight into attitudes and acceptability of pharmacogenetic testing. These will include: 1) surveys of patients and clinicians on attitudes toward pharmacogenetic testing, 2) the percent of the time in the genotype-supported arm when a dosing revision is recommended based on the patient's genotype and the clinician follows it, and 3) percentage of participants agreeing to future use of DNA for research and data sharing.

Statistical analysis. We will have two primary hypotheses tested in this pragmatic clinical trial: 1. Hypothesis: RMs (1 or 2 GOF alleles) in the genotype-supported arm have better GERD control than RMs in the usual care group 2. Hypothesis: PMs (1 or 2 LOF alleles) in the genotype-supported group have fewer adverse effects (composite of URI/GI infections, kidney adverse effects, bone fracture) than PMs in the usual care group. Continuous variables will be compared between the genotype-supported group and the usual care group using t-test, and categorical variables will be compared using the chi-squared test. The hypotheses will be tested by logistic regression analysis to estimate the odds ratios and 95% confidence intervals for GERD control rate in the RM patients between the two arms and for the adverse events between the PM patients between the two arms. Time to-event analysis will be performed using Kaplan Meier method and a Cox regression model. Significant covariates associated with the events will be adjusted for in the multivariable models. All analysis will be performed in SAS 9.4 (Cary, NC).

We will also have a composite analysis that is conducted in the same manner that combines efficacy and safety and tests the hypothesis that genotype supported PPI dosing leads to better PPI efficacy and safety, as determined by composite of refractory GERD, and adverse effects.

Finally, we will evaluate the influence of genotype-supported dosing recommendations and will evaluate the percentage of the time when a dosing recommendation was made and accepted by the treating clinician, to provide practical data on the willingness of clinicians to adopt this approach. We will also collect patient- and provider-level survey data on attitudes about pharmacogenetics testing; using survey tools adapted from those utilized by other IGNITE groups. These will be shared for network-wide analyses, but because of the number of patients we will study, we should also have sufficient data to perform analyses on our patients along.

Power calculation. Briefly, with 600 participants in the trial, we will have 80% power at alpha level of 0.05 to detect a relative risk of 1.35 or higher in the GERD control within RM patients in the usual care vs. the genotype-supported arm. This assumes that among the 600 participants, 33% will have the RM phenotype, and half will be randomized to each arm of the study. For the adverse event hypothesis, with 600 patients, we expect to have 178 PM patients, with 89 patients in each arm. At alpha level of 0.05, we will have 80% power to detect relative risk reduction of 29% or more in the adverse events for PM patients in the genotype supported group compared to those in the usual care group.

Clinical Trials.gov. This trial requires registration in ClinicalTrials.gov.

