Genotyping and result reporting. Genotyping will be done by the CLIA-licensed UF Pathology Laboratory, as has been done for over 1,600 patients in the UF Health CYP2C19-clopidogrel implementation, with genotype results reported in the EHR. For patients randomized to the genotype-supported arm, genotype results will be available in approximately 2 weeks. For patients randomized to the conventional treatment arm, the genotype results will be resulted in the EHR after the patient completes study participation (12 weeks after patient enrollment). The patient's clinician will be educated about the genotype results and their implication for PPI response. A recommendation for a dose increase will be provided for RMs and UMs (approximately 30% to 35% of patients). For patients with other genotypes, clinicians will be advised that usual PPI doses are expected to be effective that lower doses may be sufficient for symptoms management in PMs. Clinicians will also be provided quick reference guides that will include phenotype, genotype, dosing recommendations, and educational information. The PMP Committee has convened with the GI clinicians to evaluate and approve the dosing recommendations for adults based on CYP2C19 genotype. Clinical decision support tools in the EMR will also be implemented that will provide this guidance to the treating clinician. While dosing recommendations will be provided based on genotype results, the ultimate prescribing decision will be left to the discretion of the treating physician.

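### At Nemours, nothing in the plan keeps control-arm genotypes from treating clinicians during follow-up: an avoidable contamination risk of unknown size

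*Combined protocol and SAP*

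**What the plan says.** **Nemours protocol (Study Design, Focus on Aim 2).** Under Genetic results and clinical decision support: "Results will be entered in the participant's electronic health record". The Dosing subsection has all participants genotyped, so this covers both arms. For controls the stated limit is that "genotype results for participants in the control/conventional arm will not be made available to patients/families through the secure patient portal", and the reason given is to preserve the blind. The Study Design paragraph says who is blinded: "At NCH, study participants in the control/conventional arm will be blinded on CYP2C19 metabolizer status". It adds that "Study staff members will not be blinded to any study procedures or determinations".

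On timing, the CYP2C19 genotyping subsection describes the on-site assay ("Two of these rapid turnaround (approx. 1 hour) platforms reside in" the Orlando hospital) and gives about one week for samples sent to Delaware. Controls learn their status late: "At the end of study period (i.e. 8-12 weeks) study participants in the control/conventional arm will be revealed of metabolizer phenotype status". No date is given for posting a result in the EHR.

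On control-arm dosing: "Participants in the conventional arm will be prescribed the conventional PPI dose". The Dosing subsection likewise ties that arm to the FDA label. A further sentence under Genetic results confines genetic results to a secure database for study investigators.

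**UF protocol (7. Research Plan, Genotyping and result reporting).** "For patients randomized to the conventional treatment arm, the genotype results will be resulted in the EHR after the patient completes study participation", which is placed at 12 weeks after enrollment. Under Participant Recruitment Methods, a UF control may be withdrawn if the genetic test is ordered during the study.

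**The concern.** The trial compares prescribing with and without knowledge of the CYP2C19 phenotype. In an open-label design, the control condition depends on the prescriber not having that knowledge. At Nemours the concealment is aimed at families, yet it is the clinician who chooses the dose and who receives phenotype-based dosing guidance in the same EHR.

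The setting adds to the risk. The Significance section says Nemours already runs a program that lets its gastroenterologists dose by genotype, while UF gastroenterologists have not done so. The site with the weaker safeguard is therefore the one where acting on a visible genotype is most familiar.

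A control RM or UM dosed with knowledge of the genotype resembles a patient in the intervention arm. The efficacy contrast then shrinks toward no difference. The same applies to the second Nemours primary hypothesis (Statistical analysis), which compares adverse effects between arms among carriers of loss-of-function alleles. If the sites are combined, their control conditions would also differ.

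**Working it through.** **1. Who may see a control genotype, and when.**

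| | UF | Nemours |
|---|---|---|
| Result in EHR | After participation ends (12 weeks) | Yes; no time stated |
| Withheld from families | Until release | Yes, through the portal |
| Withheld from treating clinician | Until release | Not stated |
| Other access statement | None found | Study investigators only |
| Provision for a control tested or treated by genotype | May be withdrawn if test ordered | None found |

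Posting during follow-up at Nemours is an inference from two facts. The assay takes about an hour on site, or about a week through Delaware. And a portal block that preserves a blind until 8-12 weeks would be needless if results were posted only after that.

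**2. Whether contamination would be detected.** The Nemours metrics subsection counts how often a recommended dose revision is followed in the genotype-supported arm. No matching record is described for control-arm dosing.

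**3. Reproducing the plan's power figure.** Inputs from the UF Analysis Plan and Power Calculations: 90 per arm, about 30 RM/UM per arm, effect 0.74 on RDQ, alpha 0.05, power 80%. Sidedness is not stated; I assume two-sided.

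- RM/UM share from Table 1: 28% + 5.3% = 33.3%. Per arm: 0.333 × 90 ≈ 30.
- Two-sample t-test, SD = 1, noncentrality 0.74 × √(30/2) = 2.87: power 80.5% (81.8% by the normal approximation). The plan's 80% is reproduced. A one-sided test would give 88.9%, which supports the two-sided reading.

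**4. Nemours' share.** 60 of 180 patients, so 30 per arm with equal allocation within site. RM/UM: 0.333 × 30 ≈ 10 of the 30 controls, or one third. This applies the Table 1 frequencies to children.

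**5. Dilution.** Let c be the fraction of Nemours control RMs/UMs dosed by genotype. If each gains the full effect and the sites are pooled on RDQ, then pooled effect = 0.74 × (1 − c/3). No value of c is given, so the range is assumed.

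| c | Effect | Power, 30 per arm | RM/UM per arm for 80% power |
|---|---|---|---|
| 0 | 0.74 | 80.5% | 30 |
| 10% | 0.715 | 77.8% | 32 |
| 25% | 0.678 | 73.4% | 36 |
| 50% | 0.617 | 65.1% | 43 |
| 100% | 0.493 | 46.8% | 66 |

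Example, c = 25%: 0.74 × (1 − 0.25/3) = 0.74 × 0.917 = 0.678. Allowing for the extra variance of a mixed control arm lowers power slightly further, to 63.5% at c = 50% and 44.6% at c = 100%.

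**The case against.** The strongest reply is that the plan fixes the control dose twice, as the conventional dose and as the labeled dose. It describes dosing recommendations as going to clinicians of patients in the genotype-supported arm. A reader might infer from the EHR entry that the plan lets clinicians dose controls by genotype. It does not. The remark that clinicians need take no action on a returned genotype comes from the paragraph explaining why there is no DSMB. It removes a duty and does not grant discretion over control dosing. The explicit clause leaving prescribing to the physician is in the UF protocol. This objection stands: genotype-informed dosing of a Nemours control would be a deviation. A dosing instruction is still not concealment, and nothing described would show whether it was followed.

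Second, the statement limiting results to study investigators could be read as the safeguard. It conflicts with EHR entry in the same subsection. It also does not say whether treating gastroenterologists at Nemours count as investigators, as participating UF clinicians do.

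Third, the absence of staff blinding is a declared choice made for feasibility. It concerns study staff, and a reader should not take it as evidence that treating clinicians look up control genotypes.

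Fourth, the power figures borrow UF's endpoint. RDQ is not among the instruments the Nemours protocol lists, and its own power statement rests on 600 participants and relative risks. The UF power section counts all 180 patients, but its Research Plan calls Nemours a parallel study under a separate IRB protocol. This limits what the figures can show.

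**Conclusion.** The concern holds as a missing safeguard. The Nemours text does not keep control genotypes from treating clinicians during follow-up, contains two access statements that disagree, and lacks the delayed release used at UF. Entry during follow-up is a strong inference, not a stated fact.

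The direction of any bias is toward no difference, provided that genotype-informed dosing has the benefit the trial hypothesizes. The size is unknown. A reader might infer that the trial's power is in fact well below 80%; the documents do not support that. The fall to 78%, 73%, 65% or 47% rests on assumed contamination rates, full benefit in every contaminated control, and pooling on RDQ. The 47% figure requires the control dosing rule to be ignored in every Nemours control RM/UM. On the same assumptions, because power starts at about 80%, a rate of 10% is enough to take it below target. The adverse-event contrast is exposed in the same direction, but I have not quantified it.

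**What to change.** In the Nemours protocol:

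1. Adopt UF's release rule. Hold control-arm genotype results, and any phenotype-based decision support for those patients, out of the clinician-facing EHR until the patient's final study questionnaire is complete. Keep them in the laboratory or study database until then.
2. Reconcile the statement on EHR entry with the one confining results to study investigators. State who may see a control result, from when, and whether treating gastroenterologists count as investigators.
3. Record the PPI dose actually prescribed in both arms and report it by arm and phenotype, so that contamination can be detected and described.

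The cost is a few sentences of protocol text, a change in how results are released in the EHR (the documents do not describe the configuration work), and one additional data item for controls. Clinicians of control patients would receive results up to 12 weeks later, a delay the UF protocol already accepts.
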